Dose: All subjects in all groups will engage in 12 rehabilitation sessions (3x/week over 4 weeks).. Recent data suggest that the dose of practice, e.g., number of movement repetitions, is important to produce neural reorganization and motor learning.⁷¹ We therefore will provide approximately 200 reach-to-grasp/touch repetitions per session which previous research has shown to be safe for people with stroke and feasible to accomplish in 2-

3 hours.⁷² **Treatment Groups:** Targeted practice is defined as an evidence-based intervention targeted to specific UE motor deficits characteristic of persons in each UE impairment level. Non-targeted task practice is defined as a “standard of care” intervention that consists of task practice with no guidance from measurement to choose appropriate tasks to address specific underlying deficits. **Table 4** presents a summary of the treatments.

Table 4: Summary of treatments

Rasch FMA-UE Impairment Level	Rasch FMA-UE Person Measure	Targeted Treatment	Non-Targeted Treatment
Mild	>2.44 logits	Forced-use task practice	Functional Upper Extremity Training
Moderate	- 0.22 to 2.44 logits	Task practice with trunk restraint	
Severe	<-0.22 logits	Task practice with trunk restraint and faded arm support	

Targeted Practice Treatment: A person with mild UE motor impairment has a 50% probability of accomplishing FMA-UE items requiring fine motor coordination and dexterity, i.e., items well-matched to his/her ability described in Table1. For people with this level of UE motor impairment *Forced use task practice* is an optimal evidence-based intervention.⁷³ Forced use therapy, like Constraint-Induced Movement Therapy²⁸ although not delivered in its “signature” dose, restrains participants’ less affected UE in a glove to prevent its use thereby “forcing” exclusive use of the affected UE. The premise of the strategy is that repetitive object grasp, manipulation reduces “learned non-use”.⁷⁴ The intervention is shown to improve fine motor dexterity, movement speed, and smoothness.^{31,32}

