Hypothesis: People with stroke have different patterns of response to therapy, some respond slowly, some respond more quickly. Key neuromechanical variables (baseline measurements of elbow extension, amount of trunk movement, and biceps-triceps muscle co-activity) predict these response patterns.

Rationale: Individuals with different levels of post-stroke UE motor impairment likely follow distinct trajectories of UE recovery. It is possible that patients receiving intensive therapy make large improvements within the first few days of therapy, and it is also possible that some patients require days until therapy has an effect. However, little is known about patterns of recovery over time in response to rehabilitation. Identifying different patterns of recovery during therapy is critical to determine which patients may need the most extensive intervention to promote functional recovery, and which patients may not require intensive intervention. In addition, it is important to identify behavioral markers that predict gains in order to improve a-priori assessments and planning for the population that is most likely to benefit from an intervention after stroke.

Approach: Growth mixture modeling (GMM) offers a robust method of identifying sub groups of people with stroke who follow distinct trajectories of UE recovery. In contrast to analyses that focus on mean-level change in a

sample, GMM elucidates how different people recover in different ways. GMM separates repeated measurements of a sample into groups of individuals showing similar patterns of change over time.

Dependent Variable: A categorical latent variable representing unobserved groupings of stroke-patients with similar patterns of change in the Rasch FMA-UE scores over repeated measurements.

[figure not shown]
Observed Variables: The Rasch FMA-UE will be administered at 5 time periods (pre-intervention, end of weeks 1,2 and 3 and post-intervention). The GMM calculates an intercept and slope of a line representing the mean and variance of the linear rate of change in Rasch FMA-UE over time. Sub-populations (or growth classes) will be displayed graphically. Each class will represent a percentage of the sample and demonstrate how the baseline Rasch FMA-UE measurement changed over time.

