Data analysis: Data from participants in targeted-rehabilitation protocols will be pooled and analyzed. Three models will be tested in accordance with our a-priori hypothesis that each level of impairment (mild, moderate, severe) should show distinct patterns of recovery, i.e., we expect 3 classes of recovery. Specifically, we will test whether there is one overall pattern of recovery that describes the entire sample (1-class), whether there are two patterns of recovery within the sample (2-class) or whether there are three patterns of recovery in the sample (3-class). The models are not nested (a 1-class model is not a subset of the 2-class model) because different individuals make up each class. Therefore the chi-square model comparison test is not appropriate. Instead, we will define the best fitting model as the one having the lowest Bayesian Information Criteria (BIC) and an entropy value closest to 1.0.

To determine the best predictors of recovery patterns we will use logistic regression to relate recovery pattern (growth class membership) to kinematic and EMG variables hypothesized to be important predictors of recovery. The predictors hypothesized to be important are baseline elbow extension AROM, amount of trunk movement, and muscle co-activity. The predictor variables entered into analysis will be collected pre-intervention. Predictors will be examined to determine those which significantly discriminate class membership. Because the predictors are allowed to vary across classes, the analysis will provide a means of examining whether predictors of one trajectory differ across each trajectory. For example, loss of elbow extension AROM may be the most significant predictor of membership in one class, while inability to activate agonist muscles may be the most significant predictor of another recovery pattern.

Methods specific to the SUBSTUDY

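### Aim 3 asks about early versus delayed response, but its only written growth form is a straight line, whose slope does not order patients by onset

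*Protocol*

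**What the plan says.** All of this stands in the protocol, Section D, under the heading specific to Aim 3.

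- **Hypothesis:** patients differ in their pattern of response; "some respond slowly, some respond more quickly".
- **Rationale:** two contrasting patterns are described. One is early gain: "It is possible that patients receiving intensive therapy make large improvements within the first few days of therapy". The other is delayed gain: "it is also possible that some patients require days until therapy has an effect".
- **Observed Variables:** "The Rasch FMA-UE will be administered at 5 time periods (pre-intervention, end of weeks 1,2 and 3 and post-intervention"). The growth form follows: "The GMM calculates an intercept and slope of a line representing the mean and variance of the linear rate of change".
- **Data analysis:** targeted-arm patients are pooled across impairment levels. Models with one, two and three classes are compared by BIC and entropy, with the prior expectation that "we expect 3 classes of recovery", one per impairment level. Baseline kinematic and EMG variables are then related to class membership by logistic regression.

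No quadratic, piecewise or free-shape growth term is given for Aim 3. The option of a quadratic trend belongs to the Aim 2 regression. The SAP covers Aim 1 only.

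**The concern.** Early against delayed onset is a difference in the shape of the recovery curve. A straight line has no parameter for shape, and adding classes of straight lines does not supply one. Two patients who gain the same amount, one in the first week and one in the last, can receive the same slope.

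If the classes do not capture timing, the logistic regression has no timing class to predict. A report of one overall recovery pattern could then reflect the form of the model rather than the patients. The five assessments would allow a check at the weekly scale, but the plan does not call for one.

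**Working it through.** The documents give no sample size, power or residual SD for Aim 3, so there is no stated figure to reproduce. The check is algebra, backed by simulation.

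**Inputs**
- Five assessments (Aim 3, Observed Variables), coded t = 0, 1, 2, 3, 4 weeks. The coding is my assumption. It uses the four-week course in the Dose paragraph; the SAP's missing-data paragraph speaks of three weeks.
- Total gain g, the same for every patient compared.
- Pilot targeted group, for scale (Section 2h): baseline 0.90 (SD 1.01), post 2.30, so g = 2.30 - 0.90 = 1.40 logits.
- Analysis set: 3 x 18 = 54 completers, or 130/2 = 65 enrolled.

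**Formulas.** With mean t = 2 and sum of (t-2)² = 10:
- slope = sum of (t-2)y / 10
- intercept = mean(y) - 2 x slope
- quadratic coefficient = sum of w·y / 14, with w = (2, -1, -2, -1, 2)

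With balanced data, linear random effects and equal residual variances, the fitted mean line of a class equals this least-squares line.

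**Results, in units of g**

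| Pattern | Values | Slope | Intercept |
|---|---|---|---|
| All gain by week 1 | 0, 1, 1, 1, 1 | (-1+0+1+2)/10 = 0.20 | 0.8 - 0.4 = +0.40 |
| All gain by week 2 | 0, 0, 1, 1, 1 | (0+1+2)/10 = 0.30 | 0.6 - 0.6 = 0.00 |
| All gain by week 3 | 0, 0, 0, 1, 1 | (1+2)/10 = 0.30 | 0.4 - 0.6 = -0.20 |
| All gain in last week | 0, 0, 0, 0, 1 | 2/10 = 0.20 | 0.2 - 0.4 = -0.20 |
| Steady rise | 0, 0.25, 0.5, 0.75, 1 | 2.5/10 = 0.25 | 0.5 - 0.5 = 0.00 |
| One-week delay, then steady rise | 0, 0, 1/3, 2/3, 1 | 2.667/10 = 0.267 | 0.4 - 0.533 = -0.133 |

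From earliest to latest step the slope runs 0.20, 0.30, 0.30, 0.20. It varies with timing but does not rank it. The delayed starter in the last row has a steeper line than the patient who gained everything by week 1.

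**Less extreme example.** Gains of 0, 0.6, 0.8, 0.8, 0.8 and 0, 0, 0, 0.2, 0.8 logits both give slope 1.8/10 = 0.18 per week, with intercepts 0.24 and -0.16, although both start at 0.

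**Size of the intercept signal.** The gap between first-week and last-week responders is 0.40g + 0.20g = 0.60g, or 0.84 logits at g = 1.4. In the less extreme example it is 0.40 logits. Both are below the pilot baseline SD of 1.01. That pilot enrolled moderate impairment only, whereas Aim 3 pools mild, moderate and severe patients, so the baseline spread should be wider.

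**Simulation.** n = 54, half early and half late, g = 1.4, baseline SD 1.0, residual SD 0.20, 0.30 or 0.45 (assumed).
- Step curves, linear mixture, 60 runs per setting: BIC chose one class in all 180 runs. A forced two-class fit labelled 53-55% correctly, where chance is 50%.
- Less extreme curves scaled to g = 1.4, with an assumed random-slope SD of 0.1, 30 runs per setting: the linear mixture chose one class in 89 of 90 runs. With one class-specific quadratic term, BIC chose two classes in 90 of 90, with 92-99.9% labelled correctly.

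**Why the added term works.** The quadratic coefficient is -2/14 = -0.143g for all gain by week 1 and +2/14 = +0.143g for all gain in the last week. In the less extreme example it is -0.10 and +0.10.

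**Visit timing.** Equality of slopes stays exact when the pre and post visits are symmetric about week 2 (pre at -1, post at 5: 0.150g each). Otherwise it is approximate (pre at -1, post at 4: 0.189g against 0.149g).

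**The case against.** Four points can be made for the plan, and each limits the claim.

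1. **The equal slopes are a special case.** They need equal total gain, mirror-image timing, visits symmetric about the midpoint and equal residual variances. This stands. A reader might infer that early and late responders always share a slope, or that slope reflects only total change. The table shows otherwise; what remains is that slope does not order patients by onset.

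2. **The hypothesis can be read as rate.** Slow against quick may mean average rate, which a slope measures, and the expected classes follow impairment level, where intercept and rate are relevant. Onset appears only in the rationale, as a possibility. This also stands. A reader might infer that a line cannot answer the time-course question at all; only the onset part is out of its reach.

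3. **The text speaks of days and the visits are weekly.** If a delayed patient waits four days and then rises over four days (an assumption), the visit values are 0, 0.75, 1, 1, 1 and the quadratic coefficient is -1.75/14 = -0.125g, against -0.143g for an immediate responder. No growth form would separate these well on this schedule.

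4. **The remedy may not recover the classes.** At a total gain of 0.8 logits, a simplified check (a two-class mixture on each patient's quadratic contrast, n = 54, 200 runs) chose two classes in 92% of runs at residual SD 0.20, 17% at 0.30 and 3% at 0.45. A full mixture with a quadratic term did better than this at 0.30, but it too mostly failed at 0.45.

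A figure is also missing next to the sentence on the growth form. It may show the model and cannot be checked.

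**Conclusion.** The point holds in a limited form. The written model can sort patients by average rate of gain but not by onset, and its rationale asks about onset. First-week and last-week responders with equal total gain both get 0.20g per week, and their timing difference survives only as an intercept gap of 0.60g.

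A reader might expect this gap to produce false baseline classes. The simulations do not support that: the failure they show is missed classes, with one pattern reported. That result rests on the assumed residual SDs, on equal numbers of early and late patients, and on strongly contrasted curves.

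The change is worth making because the data are already planned, but it concerns the third aim only and leaves Aim 1 untouched.

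**What to change.** Before choosing the number of classes, also fit a growth form with a class-specific shape mean on the five planned assessments: either a quadratic term, or a piecewise slope with a knot at the end of week 2. Compare it with the linear form by BIC and keep the line if it fits better. State the time coding used for the pre and post visits. Hold the variance of the shape factor at zero, or equal across classes, to limit the number of parameters. State in the report that weekly assessments cannot resolve delays of a few days.

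**Cost:** no new data. There is one extra mean per class, about three for three classes. A shared random shape effect adds about three more parameters (one variance and two covariances), and a class-specific one adds more (3 x 3 = 9 for three classes). Fits will be less stable with about 54 to 65 patients, and recovery of the classes will depend on a residual SD that the documents do not give.

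### Aim 3 decides its hypothesis about the three observed impairment levels by counting latent classes, and the count cannot answer that question

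*Protocol*

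**What the plan says.** Section D of the Protocol, under Specific to Aim 3, contains two different hypotheses.

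- **Response patterns.** The labelled hypothesis is "People with stroke have different patterns of response to therapy, some respond slowly, some respond more quickly", with baseline elbow extension, trunk movement and biceps-triceps co-activity predicting the pattern.
- **Impairment levels.** The Rationale says "Individuals with different levels of post-stroke UE motor impairment likely follow distinct trajectories of UE recovery". The Data analysis paragraph makes this the a-priori hypothesis: "each level of impairment (mild, moderate, severe) should show distinct patterns of recovery, i.e., we expect 3 classes".

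The analysis set is the targeted arms ("Data from participants in targeted-rehabilitation protocols will be pooled and analyzed"), measured at five visits. The growth model has an intercept and a linear slope. The chosen model is "the one having the lowest Bayesian Information Criteria (BIC) and an entropy value closest to 1.0" among one, two and three classes. Class membership is then related to other variables by logistic regression: "The predictors hypothesized to be important are baseline elbow extension AROM, amount of trunk movement, and muscle co-activity". Impairment level is not among them.

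No other analysis relates level to the trajectory. The Protocol's Aim 1 ANOVA compares targeted with non-targeted change across the levels. The SAP nests level within treatment, assesses the main effect of treatment over Pre, Mid and Post, and has no Aim 3 section.

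**The concern.** Level is observed at baseline and is the randomisation stratum. Whether the levels recover differently is therefore a question about a known grouping factor, and it has a direct test. The plan replaces it with a question about how many unobserved groups best describe the data. Three classes need not be the three levels: the labelled hypothesis itself offers another basis, "some respond slowly, some respond more quickly".

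The classification system underlies the targeted treatments. A three-class result could be taken as evidence that the levels recover differently, and a one- or two-class result as evidence that they do not. Neither would follow.

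**Working it through.** **Inputs from the documents.** Aim 3 has no sample-size figure of its own. The Aim 1 figure reproduces: pooled SD = √((1.00² + 0.45²)/2) = 0.775; d = (2.30 − 1.42)/0.775 = 1.13; a two-sided t-test at 0.05 with 90% power needs 17.5, so 18 per group. The targeted arms then hold 3 × 18 = 54 planned completers. The level cuts are −0.12 and 2.44 logits in Preliminary Studies; Table 4 gives −0.22 for the lower cut, and the two must be reconciled. The five visits are taken as weeks 0 to 4.

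**Assumptions.** The documents give no weekly slopes, slope SD, residual SD or baseline shape for Aim 3. The table below uses residual SD 0.3 logits, slope SD 0.1 to 0.2 logits per week, 18 per level and 150 to 200 runs per setting. Mixtures have a common covariance and are chosen by lowest BIC only. Three baseline shapes were used: one normal distribution (mean 1.1, SD 1.6) cut at −0.12 and 2.44; uniform; and clustered by level. Level is assigned from the error-free baseline. The level test is an F-test of individual five-visit slopes across the levels at 0.05.

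| Mean slopes by level | Baseline | BIC picks 3 classes | Level test significant |
|---|---|---|---|
| 0.25 / 0.25 / 0.25 | normal, cut | 2% | 8% |
| 0.25 / 0.25 / 0.25 | uniform | 8.5–12% | 2.5–7.5% |
| 0.25 / 0.25 / 0.25 | clustered | 98.5–100% | 4% |
| 0.15 / 0.25 / 0.35 | normal, cut | 3% | 84% |
| 0.15 / 0.25 / 0.35 | uniform | 14% | 59.5–98.5% |
| 0.15 / 0.25 / 0.35 | clustered | 100% | 98% |
| 0.1 / 0.3 / 0.5 | normal, cut | 8% | 100% |
| 0.1 / 0.3 / 0.5 | uniform | 24–43.5% | 100% |
| 0.05 / 0.35 / 0.15 | normal, cut | 35% | 100% |
| 0.05 / 0.35 / 0.15 | uniform | 58.5–85% | 96.5–100% |

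Compare the first block (hypothesis false) with the second (hypothesis true). The three-class rate is 2% against 3% with a cut normal baseline, and 98.5–100% against 100% with a clustered one. The count follows the baseline shape far more than the slopes. It responds more when the slopes do not rise in order of level, but still not reliably.

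**A direct test needs care.** Level is cut from the observed baseline, which is also the first point of the trajectory. A five-visit least-squares slope gives each visit the weight (week − 2)/10, so baseline error enters with weight −0.2. For a patient whose observed baseline is one logit above the mean, the expected error is σe²/(σb² + σe²).

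- σb = 1.0, σe = 0.5: 0.25/1.25 = 0.20 per logit, so a slope bias of 0.20 × 0.2 = 0.04. Patients at the two cuts, 2.44 + 0.12 = 2.56 logits apart, differ by 2.56 × 0.04 = 0.10 logits per week with no true difference.
- σb = 2.0, σe = 0.3: 0.09/4.09 = 0.022, bias 0.0044, difference 0.01.

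In simulations with equal true slopes and level cut on the observed baseline (baseline SD 1 to 2, residual SD 0.3 to 0.5), the five-visit test rejected in 5% to 49% of runs. Slopes from the four post-baseline visits carry no weight on baseline and kept about 5%.

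**Price of omitting baseline.** The residual part of the slope variance is σe² divided by the sum of squared week deviations: 10 for five visits, 5 for four. At slope SD 0.15 and residual SD 0.3:

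- Five visits: 0.0225 + 0.09/10 = 0.0315; noncentrality 18 × (0.1² + 0.1²)/0.0315 = 11.4; power 84% (F on 2 and 51 df).
- Four visits: 0.0225 + 0.09/5 = 0.0405; noncentrality 0.36/0.0405 = 8.9; power 74%.

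**The case against.** **The labelled Aim 3 hypothesis is about latent response patterns, and a growth mixture with predictors of class suits it.** This stands. A reader might infer that Aim 3 as a whole has no valid test; the documents do not support that. The gap concerns the level hypothesis, which appears in both the Rationale and the Data analysis.

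**Loss of power is not established.** This also stands. A reader might infer from the table that the plan loses a definite amount of power. Every slope and variance is assumed, BIC selection is not a 5% test, and with clustered baselines the failure is false three-class results, not missed differences. The simulation also leaves out entropy, half of the selection rule.

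**A level-by-week test on all five visits can be biased.** This is correct, as the working shows, and it shapes the fix.

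**The class plots will show where each class starts, and classes are to be described by FMA-UE items on the scale that defines the levels.** An informal comparison of class with level is therefore possible. It shows starting position, though, and does not test whether the levels recover differently.

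**No passage says how a three-class result will be interpreted.** That is so; misreading is a risk created by the wording, not a stated rule.

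**Conclusion.** The concern holds for the level hypothesis only. The class count cannot support or refute it, because classes may form on baseline alone and differing slopes may be absorbed in one or two classes. That conclusion follows from the structure of the plan and needs no simulation. The frequency of a wrong reading cannot be derived from the documents: under equal slopes it ran from near 0% to near 100% across the baseline shapes tried. The percentages are illustrations that assume linear growth, complete data and independent errors between visits. The mixture remains appropriate for slow and quick responders, and the Aim 1 comparison is not affected. The change should be made, but it is not critical to the trial's main result.

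**What to change.** In the Aim 3 data analysis:

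1. Delete the clause that equates the level hypothesis with three classes. Keep the one- to three-class comparison for the response-pattern hypothesis.
2. Test the level hypothesis with a mixed model of the Rasch FMA-UE in the targeted arms. Use weeks 1, 2, 3 and post as outcomes; include level, week and level by week, with patient-level random intercept and slope. The two-degree-of-freedom level-by-week term is the test; state its alpha.
3. Report the five-visit version as a sensitivity analysis, noting that selection of level on the observed baseline can bias it through regression to the mean.
4. Report a table of class by impairment level.

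The cost is one model and one table on data already planned. Omitting baseline from the slope loses precision (84% to 74% power in the example above). It also means that the main test does not see differences between levels in the gain before the end of week 1; the five-visit analysis does, subject to its bias.

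### The Aim 3 rule for choosing the number of recovery classes joins BIC and entropy with no priority between them, although entropy does not measure fit and has no usable value for the 1-class model.

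*Protocol*

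**What the plan says.** The rule is in the Protocol, section D, under Specific to Aim 3, Data analysis. Patients from the targeted arms are pooled, and growth mixture models with one, two and three classes are compared. The investigators state an expectation in advance: "we expect 3 classes of recovery", one for each impairment level.

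A likelihood-based test is set aside on this ground: "The models are not nested (a 1-class model is not a subset of the 2-class model) because different individuals make up each class". The text continues: "Therefore the chi-square model comparison test is not appropriate". The choice then rests on one sentence: "we will define the best fitting model as the one having the lowest Bayesian Information Criteria (BIC) and an entropy value closest to 1.0".

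The protocol gives no entropy formula. It does not say how entropy applies to a single class, or which criterion decides if the two disagree. Class membership from the chosen model then becomes the outcome of a logistic regression on baseline elbow extension, trunk movement and muscle co-activity. The SAP deals with Aim 1 and missing data only, so it does not settle the matter.

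**The concern.** The two criteria answer different questions. BIC weighs likelihood against the number of parameters, so it bears on which model the data support. Entropy summarises the posterior class probabilities. A model can fit better and still classify less sharply, for instance when real classes overlap. The protocol uses both to define the best-fitting model and requires one model to win on both.

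Two difficulties follow. The 1-class model is one of the three candidates, but there is no classification in it for entropy to describe. And when 2 and 3 classes are compared, the lowest BIC and the highest entropy may belong to different models.

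The number of classes is the main result of Aim 3, and it fixes the outcome variable of the predictor analysis; with one class there would be no membership to predict. If the rule yields no answer, the choice is made after the data are seen, by investigators who have already said which number they expect.

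**Working it through.** **Inputs from the Protocol.** Candidates K = 1, 2, 3; rule and exclusion of the chi-square test as above (Specific to Aim 3, Data analysis). Five measurement times and linear trajectories (Specific to Aim 3, Observed Variables). Planned evaluable patients 18 per group (section D, sample size), so the three targeted groups give 3 × 18 = 54. The plan states no figure for this rule, so there is none to reproduce.

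**Assumed.** The usual relative entropy, since the protocol gives no formula:

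E(K) = 1 − [Σᵢ Σₖ (−pᵢₖ ln pᵢₖ)] / (n ln K), where pᵢₖ is the posterior probability that patient i belongs to class k.

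**Step 1: one class.** Every p is 1, so the numerator is 0. The denominator is 54 × ln 1 = 0. E(1) is therefore 0/0. It equals 1 only if one adopts the convention that no uncertainty counts as perfect.

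**Step 2: two classes.** Suppose every patient's larger posterior probability is p. Then E(2) = 1 + [p ln p + (1 − p) ln(1 − p)] / ln 2. At p = 0.99 this is 1 − 0.0560/0.6931 = 0.919.

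| p | 0.999 | 0.99 | 0.95 | 0.90 |
|---|---|---|---|---|
| E(2) | 0.989 | 0.919 | 0.714 | 0.531 |

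E depends only on the posterior probabilities. The likelihood of the model does not enter it.

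**Step 3: what the rule returns on each reading.**

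- E(1) set to 1 by convention: a 2- or 3-class model with any classification uncertainty falls below 1, so it can at best tie after rounding.
- E(1) left undefined: the 1-class model cannot meet the entropy condition, so the rule cannot select it even when BIC does.
- Entropy compared only for K ≥ 2: a multi-class model can meet both conditions, but 2 against 3 classes can be left undecided.

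**Step 4: can BIC and entropy disagree in data of this size?** A simulation took 54 patients, 18 in each of three true classes, at times 0 to 4, with slope SD 0.06 and residual SD 0.25. Class mean (intercept, slope) pairs in logits were (−1.2, 0.1), (1.1, 0.25), (3.2, 0.1) with intercept SD 0.35 (well separated) or 0.6 (moderate). For the overlapping case they were (−0.6, 0.05), (1.1, 0.25), (2.6, 0.1) with intercept SD 0.8. All these values are assumed. Models were fitted by EM with a common covariance and 12 data sets per scenario. BIC was compared over K = 1, 2, 3 and entropy only over K = 2, 3.

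| Scenario | Lowest-BIC model also had the higher entropy | Disagreements | Median E(2) | Median E(3) |
|---|---|---|---|---|
| Well separated | 12 of 12 | none | 0.960 | 1.000 |
| Moderate | 6 of 12 | 6: BIC chose 3, entropy chose 2 | 0.930 | 0.915 |
| Overlapping | 7 of 12 | 5: BIC chose 1, which has no entropy | 0.898 | 0.803 |

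A second simulation of the same design, with its own assumed separations and 25 data sets per scenario, gave agreement in 25, 14 and 5 of 25. Both show that agreement and disagreement are possible. Neither estimates how often disagreement would occur in this trial.

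**Step 5: nesting.** Nesting is a relation between parameter spaces and does not depend on who is assigned to which class. A 2-class model with equal class parameters, or with one mixing proportion set to zero, is the 1-class model, so the models are nested. At that point a proportion lies on its boundary, or the class parameters are not identified. The ordinary chi-square reference distribution then fails. The protocol's decision not to use it is right; the reason given is not.

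**The case against.** The best defence is that an analyst would read the rule sensibly: entropy only where there is a classification to judge, and BIC across all three models. On that reading a 2- or 3-class model can satisfy both conditions, and with well-separated classes it did so in every simulated data set. That stands. It also disposes of a stronger conclusion that a reader might draw, namely that one class always has entropy 1 and so no 2- or 3-class model could ever be chosen. The documents state no such convention, and the usual formula is undefined at K = 1. A tally of conflicts made under that convention would merely count how often BIC prefers more than one class.

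The sensible reading is not what the protocol says, however, and it does not remove the problem. It still leaves 2-against-3 conflicts open, and it does not say what happens when BIC picks one class.

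It is also fair that the nesting error changes no planned analysis, that the simulations rest on few data sets and chosen separations, and that Aim 3 is confined to the targeted arm. These points limit the weight of the concern. They do not supply the missing priority.

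**Conclusion.** The concern holds in a limited form. The rule uses a measure of classification clarity as a criterion of fit, applies it to a 1-class model for which it is undefined or uninformative, and gives no order of precedence if it disagrees with BIC. It works when classes are well separated and can name no winner when they are not. The frequency cannot be stated from the documents: agreement ran from every data set down to 5 of 25 over the separations tried. The conclusion rests on the usual relative entropy, and the simulated counts also rest on a linear mixture with common covariance and 54 evaluable patients.

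The consequence is confined to the Aim 3 class count and the logistic regression built on it. The Aim 1 treatment comparison and the sample size are not touched. It should be corrected because the remedy is simple and the ambiguity would otherwise be resolved after the results are known.

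**What to change.** In the Protocol, section D, Specific to Aim 3, Data analysis:

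1. Select the number of classes (1, 2 or 3) by lowest BIC alone.
2. Give the entropy formula, and report entropy only for models with two or more classes, as a description of how clearly patients are classified.
3. Replace the statement that the models are not nested. Say that they are nested but that the ordinary chi-square reference distribution does not apply, and keep the decision not to use that test.
4. Optionally, add a parametric bootstrap likelihood-ratio test of K against K − 1 classes and a minimum class size fixed in advance, as support for the BIC choice.

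Items 1 to 3 cost a few sentences. Item 4 adds some computing time. No data collection changes.
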